6.5 Blinding and Unblinding

Blinding:

This study will be conducted as a double-blind study. Subjects in three arms will receive either study medications or placebo from subject kits (IMP Kit) which are identical and labeled in a manner to maintain the blind.

CONFIDENTIAL

Subjects entering the study will be randomized in ratio of 1:1:1 for 3 treatment arms.

Knowledge of the randomization list will be limited to the persons responsible for the creation of the randomization list, labeling, packing & distribution of the IMP's.

Randomization schedule will be generated based on the randomization request details and study design outlined in the protocol using SAS by the statistician & will be used to assign subjects to treatment groups. Randomization schedule will be shared with the unblinded team involved in labeling, packaging, distribution of investigational products by the statistician. Unblinded personnel at packaging site will pack the IMP's based on the randomization schedule. All the IMP's will be identified with their respective kit numbers.

To maintain the blinding through packaging:

- a. Packing material should be similar in colour and size.
- b. Labelling and packaging shall be performed as per the instructions given in the batch packaging document.
- c. Uniformity shall be maintained during assembly of labels on units, placement of units in the carton & sealing of the subject kits.

IMP's will be distributed to sites along with corresponding respective blinded labels containing the randomized treatment.

Site personnel will pick the appropriate next numbered IMP kit and complete the details on the IMP tube label dispensed. Site personnel will dispense to the subject/guardian specific IMP tube(s) and instruct the subject/guardian on the IMP usage. Subjects/guardians are advised to return the used & unused IMP tubes.

Unblinding:

In the case of an emergency, the investigator may learn the treatment arm the subject was randomized to by removing the occlusive tube label remaining in the subjects records stored at the investigator's site. Except in the circumstances detailed in unblinding section (breaking the blind), the code will not be broken. The CRO shall be contacted before unblinding whenever possible.

Unblinding a subject's treatment is restricted to emergency situations and should only be done to facilitate the proper care of a subject. In-case of emergency, investigator/authorized personnel will contact the CRO for unblinding the subjects by submitting the Un-blinding Request Form. The investigator should always attempt to contact the medical monitor/designee before breaking the blind.

CONFIDENTIAL

In case of safety issues, a medical emergency where the identity of investigational product is essential for medical management of a subject, or an AE/SAE that requires expedited reporting, shall a subject become un-blinded as to the treatment they are receiving. The unblinding provides the information about the identity of study drug provided to the subject as per the randomization list.

If there is a medical emergency with a subject, the Study PI will take the necessary medical action to address the emergency first, and then send an unblinding form to the unblinded person at CRO. Unblinded person sends this form to the medical monitor/designee for approval. If the medical monitor or designee, after careful consideration of the circumstances, feels that there is a need to know which treatment group the subject is in, he/she will approve the unblinding by signing this form. This signed /approved form will be sent to the site, upon which investigator can unblind the subject. Based on the authorization from the unblinded authority of CRO, the study PI will access to unblind the particular subject ID.

Should the unblinding happen, the same treatment kit should be withdrawn from the subject. The kit should be quarantined with proper status on site.

An account of all broken or unbroken codes will be collected by the monitor at or after site closure.

Every attempt will be made to maintain the blinding throughout the study. In any case treatment code is broken; the un-blinding procedure must be adequately documented in the subject's study file.

Before breaking the blind of an individual subject's blinded treatment, the investigator should have determined that the information is necessary, i.e., that it will alter the subject's immediate management. Every attempt will be made to maintain the blind throughout the study.

If the treatment blind is broken, the investigator will record the reason and date, time on the appropriate CRF. If the blind is broken because of an AE/SAE, an AE/SAE form will be completed and informed to CRO. Randomization data are kept strictly confidential, and are accessible only to authorized personnel, until unblinding of the trial after database lock.

7 SAFETY ASSESSMENT

Adverse event (or adverse experience, AE): Any untoward medical occurrence in a subject or clinical investigation subject administered the test and reference product which does not necessarily have to have a causal relationship with this treatment. An AE can therefore be any unfavourable and unintended sign (including for example an abnormal laboratory finding), symptom or disease temporally associated with the use of the test and reference

CONFIDENTIAL

Version 2.0 Dated 14 Oct 2016

product, whether or not considered related to the test and reference product. Each subject will be carefully monitored for the development of any adverse events. This information should be obtained in the form of non-leading questions (e.g., "How are you feeling?") and from signs and symptoms detected during each examination, observations of the study personnel or spontaneous reports from the subjects.

Subjects will be monitored for safety and tolerability during the study and until the completion of the study. Any AEs, including either observed or volunteered problems, complaints, signs or symptoms, occurring during the course of the study or designated follow-up periods, must be recorded on the subject's CRF. This would include AEs resulting from concurrent illnesses, reactions to concomitant medications.

Each AE will be evaluated for duration, intensity, and relationship to (or association with) the study treatment (or other causes). Additionally, the actions taken (e.g., discontinuation of study medication, administration of treatment) and the resulting outcome of the AE should be indicated on the CRF.

Any subject who is withdrawn from the study due to an adverse event should be followed until the outcome of the event is determined, and the investigator will prepare a written summary of the event and document the available follow-up information in the study documents.

7.1 Intensity of Adverse Events

The intensity of the AEs will be graded according to the following criteria:

- a. Mild: Events that are usually transient; require only minimal treatment or therapeutic intervention; do not generally interfere with usual daily activities.
- b. Moderate: Events that are alleviated with additional specific therapeutic intervention; interfere with usual daily activities, causing discomfort but pose no significant or permanent risk or harm to the subject.
- c. Severe: Events that require intensive therapeutic intervention; interrupt usual daily activities, or significantly affect clinical status; pose a significant risk or harm to the subject and hospitalization may be required.

7.2 Causality Assessment

Causality denotes the relation of the event to the study drug and is classified as follows by the investigator:

a. 'Definitely Related' when the AE is clearly related to the study drug or intervention and is defined as meeting all the following conditions:

Has a reasonable temporal relationship to the investigational agent(s) or research intervention; could not have been readily produced by the subject's clinical state or have been due to environmental or other intervention; disappears or decreases with reduction in investigational agent or cessation of intervention; recurs with re-exposure to the

CONFIDENTIAL

Version 2.0 Dated 14 Oct 2016

investigational agent(s) (in case of studies involving multiple administration of drug); no alternative cause is present; follows a known pattern of response to intervention

b. 'Probably Related' when the AE is likely related to the investigational agent(s) or intervention and is defined as meeting any three of the following conditions:

Has a reasonable temporal relationship to the investigational agents(s) or research intervention; Could not readily have been produced by the subject's clinical state or have been due to environmental or other intervention; Follows known or suspected pattern of response to intervention; Disappears or decreases with reduction in investigational agent or cessation of intervention; Alternative cause may be present

c. 'Possibly Related' when it may be related to the investigational agent(s) or intervention and is defined as meeting any two of the following conditions:

Has a reasonable temporal relationship to the investigational agents(s) or research intervention; Could not have been produced readily by the subject's clinical state or have been due to environmental or other intervention; Follows known or suspected pattern of response to intervention; Alternative cause is present

d. 'Unlikely Related' when it is doubtfully related to the investigational agent(s) or intervention and is defined as meeting any two of the following conditions:

Has a temporal relationship to the investigational agents(s) or research intervention; Could readily have been produced by the subject's clinical state or have been due to environmental or other intervention; Does not follow a known pattern of response to intervention; Does not reappear or worsen with reintroduction of intervention (in case of studies involving multiple administration of drug); Alternative cause is present

e. 'Not related' when the AE is clearly not related to the investigational agent(s) or intervention and is defined as meeting all of the following conditions:

Has no temporal relationship to the investigational agents(s) or research intervention; Follows no known or suspected pattern of response; Alternative cause is present.

7.3 Frequency

i.If the same type of AE occurs only once will be documented as 'Single Episode'. ii.If the same type of AE occurs more than once, will be documented as 'Recurrent'. iii.If an AE is still continuing (not resolved) will be documented as 'Continuous Event'.

7.4 Serious Adverse Events

A serious adverse event (SAE) is defined as any event that suggests a significant clinical hazard, contraindication, side effect, or precaution. This includes any event which:

- Results in death.
- Life threatening.
- Results in persistent or significant disability / incapacity.
- Requires repeated hospitalization or prolongation of existing hospitalization.

- Results in congenital anomaly / birth defect.
- Is an important medical event which includes other events, based on medical judgment, which jeopardize the subject and require medical or surgical intervention to prevent one of the outcomes listed above.

The investigator or a suitable designee will record all adverse events observed, either queried or spontaneously reported by the subject(s).

The Serious Adverse Event Reporting will be in compliance with the local legal and regulatory requirements.

The adverse events will be followed until resolution or to the satisfaction of the investigator(s) unless the subject's is deemed lost to follow-up.

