4.4 Ethical and Regulatory Considerations

4.4.1 Declaration of Helsinki and ICH-GCP

The study will be conducted according to the protocol and to guidelines from the International Conference on Harmonization (ICH) for Good Clinical Practice (GCP) in clinical trials and in compliance with all relevant local guidelines. Written approval will be obtained from the IRB prior to recruitment of subjects into the study and for all relevant material like the protocol, written subject information and informed consent form prior to recruitment into the study.

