10 STUDY ADMINISTRATIVE PROCEDURES

10.1 Regulatory Authority Approval

The Sponsor / CRO will obtain approval to conduct the study at each site from the relevant local regulatory authorities, in accordance with applicable regulatory requirements prior to initiating a site. The study will be performed in compliance with ICH-GCP guidelines and local guidelines.

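### The SAE definition names repeat or prolonged hospitalization but not a first admission, which is left to judgement

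*Protocol*

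**What the plan says.** Protocol 7.4 defines a serious adverse event by a general lead-in followed by a list. The lead-in reads: "A serious adverse event (SAE) is defined as any event that suggests a significant clinical hazard, contraindication, side effect, or precaution". The list is introduced as inclusive. It names death, threat to life, lasting or significant disability, hospitalization of a stated kind, congenital anomaly, and important medical events.

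The hospitalization bullet reads: "Requires repeated hospitalization or prolongation of existing hospitalization". The important-medical-event bullet rests expressly on medical judgement and covers events "which jeopardize the subject and require medical or surgical intervention to prevent one of the outcomes listed above".

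On reporting, the same section adds: "The Serious Adverse Event Reporting will be in compliance with the local legal and regulatory requirements".

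The only other mention of hospitalization in the Protocol's safety section is in 7.1, where the severe grade includes events that "pose a significant risk or harm to the subject and hospitalization may be required".

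The SAP has no definition of its own. SAP 10.9.1 takes seriousness and its criteria as recorded, counts subjects with any serious TEAE, and compares that incidence between test and reference with Fisher's exact test.

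**The concern.** As written, the criterion separates two kinds of admission. A repeat or prolonged stay is serious because the Protocol names it. A first stay of ordinary length is not named. That is probably the commoner kind here: participation lasts at most 32 days, a prolonged stay needs a subject already in hospital, and a repeat stay needs an earlier one. This ordering is an inference; the documents do not quantify it.

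What is at stake is consistent classification across sites. A first admission judged non-serious would be absent from:

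- the serious-TEAE count in SAP 10.9.1 and its Fisher comparison;
- the Serious AE row of Table 14.3.1.1;
- Listing 16.2.7.2.

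It might also not be handled as an SAE for reporting. Comparing the safety of test and reference is a stated objective (Protocol 2.2, SAP 2), so this count is one the study intends to use.

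**Working it through.** The plan gives no figure to reproduce. The check is to take a first, non-prolonged admission with no death, threat to life, disability or birth defect, and test it against each relevant text.

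| Text | Does it make this admission serious? |
|---|---|
| Protocol 7.4, hospitalization bullet | No. The stay is neither repeated nor prolonged. |
| Protocol 7.4, death, life-threat, disability and congenital-anomaly bullets | No, by construction of the case. |
| Protocol 7.4, important-medical-event bullet | Only by medical judgement, and only where intervention was needed to prevent an outcome listed above it. A first admission is not itself among those outcomes, though a repeat or prolonged one is. |
| Protocol 7.4, lead-in | Only if someone decides the event suggests a significant clinical hazard or one of the other general terms. |
| Protocol 7.1, severe grade | No. It grades intensity and does not state seriousness. |
| SAP 10.9.1 | No. It uses the recorded classification. |

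Two routes remain, and both need a judgement.

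**Where the event would go if judged non-serious.** It would still be recorded as an AE and appear in Listing 16.2.7.1, with its SAE entry reading No. That shell has no hospitalization column. An admission might be written under other action taken, but nothing requires it.

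**Size.** Planned numbers are from Protocol 9.1 and SAP 6: 648 subjects, 216 per arm.

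- One event: 1/648 = 0.154% of all subjects; 1/216 = 0.463% of one arm. The Safety population cannot exceed the number randomized, so at the planned enrolment these are the smallest values one event can take. Protocol 9.1 calls 648 approximate, so they would be slightly lower if more were randomized.
- Assumed first-admission rates over the 14 (± 3) day treatment period, not from the documents: 0.1% × 648 = 0.65; 0.5% × 648 = 3.24; 1.0% × 648 = 6.48 subjects. The number misclassified would be some unknown fraction of these.
- Effect on the Fisher comparison: with one event among 432 subjects in two equal arms, each arm has probability 216/432 = 0.5 of holding it, so the two-sided p-value is 0.5 + 0.5 = 1. A single reclassified event changes the count but not the inference.

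**The case against.** The strongest reply is that the definition is not closed. The lead-in is broad, the bullets only illustrate it, and the important-medical-event bullet covers intervention to prevent a listed outcome. The wording for severe events in 7.1 is close to the lead-in, so many severe first admissions would probably be classed as serious anyway. That stands, and it narrows the gap. It does not supply a named criterion, which is what makes sites classify alike.

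A second reply is that outside obligations cover the case: local requirements for SAE reporting, and the commitment in Protocol 10.1 that "The study will be performed in compliance with ICH-GCP guidelines and local guidelines". These may limit the consequence. The first concerns reporting, the second is general, and neither restates the definition that sites read.

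A third reply is that the effect may be small or absent in practice. The CRF and the AE/SAE form are not among the documents and may already list initial hospitalization. Listing 16.2.7.1 shows severity, outcome and other action taken, and Protocol 8.3 and 8.4 provide for source verification and monitoring. All of this is fair. These safeguards help to find such events, but they do not correct the rule against which the events are judged. It is also true that the assumed admission rates do not show that even one event would be misclassified.

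Finally, the wording may be a drafting slip, and the documents contain no contradictory statement. Nothing in them corrects it, and no reason is given for leaving first admissions out.

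**Conclusion.** The concern holds. Under Protocol 7.4, a first, non-prolonged admission that meets no other bullet is an SAE only by judgement, while a repeat or prolonged stay is one by name. It is not claimed that such an admission can never be an SAE, or that the event would be lost.

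The effect is confined to consistent SAE classification and what depends on it: SAE handling, the serious-TEAE count and the SAE listing. The number of events at risk cannot be derived from the documents. On the assumed rates there would be between under one and about six or seven first admissions in the whole study, with misclassifications some fraction of that. The primary equivalence and superiority analyses do not use seriousness and are unaffected. The practical effect would be smaller if the CRF already lists initial hospitalization, which cannot be seen here.

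**What to change.** Reword the hospitalization bullet in Protocol 7.4 along these lines: *Requires inpatient hospitalization (initial or repeated) or prolongation of existing hospitalization.* Then:

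1. Notify the sites of the corrected wording.
2. Check that the CRF seriousness field, which feeds the SAE-criteria columns of Listings 16.2.7.1 and 16.2.7.2, uses the same wording.
3. If subjects are already enrolled, re-check AEs that involved an admission against the corrected wording before database lock. AEs graded severe, or with an admission noted under other action taken, are a sensible place to start. Source records are needed to complete the check, because the listing does not record hospitalization systematically.

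The cost is a one-line protocol correction, a site note, a CRF check and, if enrolment has begun, a short source review. The downside is possibly slightly more SAE reports. No efficacy analysis changes.

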8 DATA HANDLING, RECORDING AND QUALITY ASSURANCE

8.1 Data Handling and Record Keeping

The investigator must ensure that proper source documentation for all activities performed in relation to this study are diligently maintained and securely kept. The investigator will transfer all relevant data from the source documents to the CRF as stipulated in this study protocol and his/her signature on the CRF guarantees the completeness and integrity of these data. All records and documents pertaining to the study will be maintained as documented for at least a period of 2 years following the date a marketing application is approved for the indication for which it is being investigated; or if no application is to be filed or if the application is not approved for such indication, until 2 years after the investigation is discontinued and regulatory authorities are notified. These documents should be retained for a longer period if required by an agreement with the sponsor. In such an instance, it is the responsibility of the sponsor to inform the investigator / institution as to when these documents no longer need to be retained.

8.2 Access to Source Data

The investigator must ensure that institutional regulations and the informed consent form clearly permit study-related monitoring, audits, IRB review, and regulatory inspections providing direct access to source data and documents by the sponsor, the sponsor's delegates, the US FDA, local regulatory bodies, or the IRB.

8.3 Source Data Verification and on-site Audits

Besides regular source data verification by the study monitor, regulatory authorities, the IRB, and/or the sponsor's personnel or designate may request access to all source documents, CRFs, and other study documentation for on-site audit inspections. The Investigator, who must provide support at all times for the activities, must guarantee direct access to these documents.

CONFIDENTIAL

Version 2.0 Dated 14 Oct 2016

8.4 Monitoring

The study will be monitored by the CRO, Sponsor, and/or Sponsor Delegate. Monitoring may be done by personal visits by the site monitor who will review the CRFs and source documents, and/or by frequent communications (letter, email, telephone, and fax). The site monitor will ensure that the investigation is conducted according to protocol design and regulatory requirements.

8.5 Data Management

Data management will ensure that clinical parameters collected on each subject throughout the study are as complete, accurate and of the highest quality possible and that the procedures are performed in accordance with all applicable guidelines and regulations (including ICH guidelines). CRFs, questionnaires and treatment diaries shall be made available to the data management site.

9 DATA ANALYSIS AND STATISTICAL CONSIDERATIONS

The following information provides an overview of the issues related to the analysis of data collected during the study.

9.1 Determination of Sample Size

The primary statistical analysis of interest is the proportion of subjects in the PP population with a clinical response of treatment success (at least an Investigator's Global Assessment of Clear or Almost Clear) at study Day 15. Considering the pivotal studies of the Reference Listed Drug, it is assumed that the active test and RLD will have approximate success rates at 21% and the vehicle cream will have an approximate success rate of 9%. A sample size of 184 subjects per group will provide at least 99% power to demonstrate bioequivalence (i.e., the 90% confidence interval (Yates' continuity -corrected) of the absolute difference between the test and reference composite success rates is within a defined equivalence range [-0.20, +0.20]). Assuming the conversion rate from mITT to PP will be about 90%, 205 subjects in each of the groups of the mITT population will provide at least 85% power to demonstrate superiority of active over placebo. Under the above assumptions, the overall global study power to demonstrate bioequivalence and superiority is estimated to be approximately 85%. To allow for about 5% of subjects who may drop out from the study or are otherwise non-evaluable, approximately 648 subjects will be enrolled (216 in each active group and 216 in the placebo group).

